We will enroll 20 female subjects who fulfill the inclusion and exclusion criteria for a 52 week study (48 weeks treatment, 4 weeks post treatment follow-up). Ten women who self identify as frequently wearing toenail polish will be placed into the study group, while the control group will be comprised of 10 women who agree to abstain from wearing toenail polish during the length of the study. To avoid having a significant gender difference between both groups, male patients will be excluded since they would likely be exclusively placed into the control group. Because nail size is proportional to body size, with men having larger nails on average, excluding men will prevent introduction of bias in this study. Patients with symptomatic tinea pedis at screening will be treated with Luzu for 2 weeks.

Treatment methods will be similar to those described by Elewski, *et al.* Briefly, all patients will self-apply 1 drop of efinaconazole 10% solution to the hyponychium and undersurface of the nail every night before bed. Patients in the study group will not be restricted with respect to the brand of nail polish, however gel and plastic based polishes that are used in salons and that require curing will be prohibited. Patients in the study group will also be permitted to touch up their polish if needed in the morning without constraint.

Patients will be seen in clinic for this study at screening and then again at baseline. After baseline, patients will be clinically evaluated every month for the first 3 months, followed by 8-week intervals, with the final visit at week 52. Our primary outcome, compatibility of topical efinaconazole solution with wearing polish, will be assessed at every visit.

An interim analysis of our primary outcome will be performed at 3 months and these results will be presented in poster and oral format as well as submitted in manuscript form for publication in a peer reviewed journal. We hope to present these data as oral and poster presentations at the summer AAD, the Fall Clinical Dermatology Conference or other similar national meeting. We will also submit a manuscript regarding the compatibility of treatment with nail polish for publication in an appropriate dermatology journal for US audiences. At the conclusion of this study we will present our findings in poster and oral format, as well as submit a manuscript for publication in the Journal of The American Academy of Dermatology.

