Subjective effect of the medication on polish will be assessed with the following series of questions to which patients can answer yes or no:

- Were you able to apply the medication under your nail?
- Are you overall satisfied with Jublia?
- Is your polish tacky in the morning?

Patients will also answer the following question, which will be answered using a Likert or VAS scale where 0 represents no alteration in polish and 10 represents complete destruction of the polish:

- Is the quality of your polish diminished with use of Jublia?

We anticipate that some patients may note diminished quality of polish with use of Jublia on a daily bases, however we anticipate that this effect will be minimal.

Secondary outcomes will include efficacy and safety. Using 3rd party blinding, DLSO will be assessed at baseline and at every subsequent visit using the onychomycosis severity index, measuring percent of the target nail involved, and grading the infection from mild to moderate to severe. The target nail will be notched at baseline, thereby allowing overall nail growth to be assessed at each visit and disease free nail growth to be measured every 8 weeks. Photos of the nails will be taken every 8 weeks, including close up photos of the target nail with and without an outline of the onychomycosis. Fungal testing will be done at screening, 3 months, 7 months, end of treatment (48 weeks), and end of study (52 weeks). Clinical and mycologic cure will be evaluated at week 52. Mycology cultures will be processed at the fungal lab of the University of Texas, with whom the UAB Dermatology Research unit has a contract. The following will comprise our inclusion and exclusion criteria:

Inclusion:

- Female age 18-75,
- Clinical diagnosis of DLSO affecting at least 1 great toenail diagnosed with positive potassium hydroxide microscopy. A culture for a dermatophyte will be collected but positive culture is not necessary for inclusion in the study. Cultures for patients with a previous positive culture can be waived at the discretion of the investigator.
- Suitable for application of topical antifungal therapy, in the opinion of the investigator
- Target toenail thickness of 3mm or less as measured by digital caliper, as thickness greater than 3mm may allow inclusion of patients with severe onychomycosis, and this was the criteria used in the pivotal trial using topical efinaconazole for onychomycosis (Elewski BE, et al.)

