- Women of childbearing potential will be required to use birth control and a negative urine pregnancy test must be documented prior to initiating treatment

Exclusion

- History of immunosuppression or concurrent use of immunosuppressant drugs
- History of uncontrolled diabetes mellitus
- History of psoriasis or any other condition that might interfere with the toenail evaluation
- Three or more dermatophytomas (streaks) on the target nail
- Severe DLSO of the target nail
- Patients who cannot refrain from wearing gel or plastic based polishes that are used in salons and that require curing

Conclusion

Treatment options for DLSO has until recently been comprised primarily of oral medications that were associated with significant possible toxicities. New research has revealed topical efinaconazole 10% solution (Jublia) to be a promising alternative treatment for DLSO, however it is unknown if this treatment is both compatible and efficacious in persons wearing toenail polish. Our proposal aims to examine the compatibility and efficacy of wearing polish while using efinaconazole 10% solution for DLSO.

Citations

Elewski BE, *et al.* Efinaconazole 10% solution in the treatment of toenail onychomycosis: Two phase III multicenter, randomized, double-blind studies. *J Am Acad Dermatol.* 2013 Apr;68(4):600-8.

Sporanox (itraconazole) [package insert]. Titusville, NJ: Janssen Pharmaceuticals Inc; 2012.

Lamisil (terbenafine HCl) [package insert]. East Hanover, NJ: Novartis Pharmaceuticals Corp; 2012.

Evaluating the Efficacy and Compatibility of Eflaconazole 10% Solution (Jublia) for the Treatment of Toenail Onychomycosis in Patients Wearing Toenail Polish Compared to Those Without Polish

NCT03110029

Statistical analysis consisted of 2-tailed T-tests to study associations between continuous variables. P-values less than 0.05 were considered statistically significant.

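### Eligibility sets no minimum target-nail involvement, so barely affected nails can enter and carry little information on whether polish reduces improvement in percent involvement, a secondary outcome.

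*Combined protocol and SAP*

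**What the plan says.** The Inclusion list asks for "Clinical diagnosis of DLSO affecting at least 1 great toenail diagnosed with positive potassium hydroxide microscopy"; a positive culture is not required. It then sets an upper limit, "Target toenail thickness of 3mm or less as measured by digital caliper", and explains it as a guard against severe disease. The Exclusion list adds two more upper limits: three or more dermatophytomas on the target nail, and "Severe DLSO of the target nail". Neither list gives a minimum percent involvement, severity-index score or grade, or a reason for having none.

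Under Methods, efficacy and safety are secondary to polish compatibility. Efficacy is assessed under third-party blinding at baseline and each later visit by the onychomycosis severity index, by "measuring percent of the target nail involved", and by a mild-to-severe grade. Nail growth, fungal testing and week-52 cure are also recorded.

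The groups are not randomised: "Ten women who self identify as frequently wearing toenail polish will be placed into the study group", and "the control group will be comprised of 10 women who agree to abstain from wearing toenail polish". The Research question states the expectation that polish will not impair treatment. The statistical section names two-tailed t-tests and adds that "P-values less than 0.05 were considered statistically significant". It gives no analysis scale, baseline adjustment, margin or power.

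**The concern.** A nail with 5% involvement can improve by at most 5 points. Whether or not polish weakens the drug, its change in involvement will be small, so it contributes little to a comparison of mean improvement. Such nails pull the mean difference towards zero if both groups contain them in similar numbers.

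That matters because the trial hopes to find no difference and tests for one with an unadjusted t-test in 10 versus 10. Without a margin, a diluted and non-significant difference may be read as support for the hypothesis. Because women choose their group, mild nails may also collect in one of them. The raw comparison would then reflect the starting point as well as any effect of polish.

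**Working it through.** **The plan's own figure.** The 20 women come with no power, effect size, SD, dropout or margin, so the number cannot be reproduced. What can be computed is what 10 per group detects. A two-sided t-test at 0.05 has power of about 18%, 40% and 56% for true differences of 0.5, 0.8 and 1.0 SD. It reaches 80% only at about 1.32 SD.

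**Inputs.** From the documents: 10 per group, two-sided 0.05, t-test. Assumed, because the documents give none: baseline involvement uniform from a lower limit L to 50%; mean clearing of 60% of baseline without polish and 30% with it; between-woman SD of that fraction 0.3; measurement SD 4 points; week-52 involvement kept within 0 to 100%.

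**Effect of the lower limit.** Raw change is baseline minus week-52 involvement. Before the bounds apply, the expected difference is (0.60 − 0.30) × mean baseline:

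- L = 1%: 0.30 × 25.5 = 7.65 points
- L = 10%: 0.30 × 30 = 9.0 points
- L = 20%: 0.30 × 35 = 10.5 points

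Not letting involvement fall below zero trims these slightly. By simulation (20,000 trials per setting):

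| Lower limit | Difference (points) | Power, raw change | Power, baseline-adjusted |
|---|---|---|---|
| 1% | about 7.2 | about 27% | about 36% |
| 10% | about 8.5 | about 35% | about 41% |
| 20% | about 9.9 | about 45% | about 47% |

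With a larger assumed harm (70% versus 20% clearing, measurement SD 5), power on raw change is about 56%, 72% and 83%; with adjustment it is about 71%, 80% and 85%.

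**How much adjustment recovers.** In the first scenario the 20% limit gains 45 − 27 = 18 percentage points unadjusted. Adjustment alone, with no floor, gains 36 − 27 = 9, about half. Once the analysis is adjusted, the floor adds 47 − 36 = 11.

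**Percent change as the scale.** With the same measurement error, power is about 29% at a 1% limit and 51% at 20%. With no measurement error, a separate illustration (baselines of 35% or 5%; mean response 50% without polish, 25% with; SD 30 percentage points) shows no dilution: power stays at 42% whatever the share of mild nails. The scale removes the problem only if involvement is measured almost without error.

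**Uneven mix, in that same illustration, on raw change.**

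- Half of controls mild, no wearers mild: means 0.5 × 20 = 10 and 0.25 × 35 = 8.75, a difference of 1.25 points instead of 8.75. Power to show harm is about 3%.
- No controls mild, half of wearers mild, polish without effect: 0.5 × 35 − 0.5 × 20 = 7.5 points. Harm is declared about 35% of the time.

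**Cure.** Assume cure of 20% versus 5% in the other nails: power is 17% with no mild nails. With half the nails mild and 60% of those cured in both groups, the rates are 40% and 32.5% and power is 5%. If polish lowers cure of mild nails to 30%, the rates are 40% and 17.5% and power is 19%.

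**Women already enrolled.** If 30% of nails are at 1-10% involvement and the rest at 20-50%, leaving out nails below 20% gives power of about 30%; keeping everyone and adjusting for baseline gives about 35%. With baseline uniform over 1-50%, the figures are about 26% and 36%.

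**The case against.** A reader might infer that near-clear nails cannot show harm. The documents do not support that. Every eligible nail has clinical disease and positive microscopy. Over 52 weeks it can worsen, stay mycologically positive or fail cure, and mycologic outcomes are not capped by percent involvement. A reader might also infer that the missing floor always favours a finding of no harm. The uneven-mix and cure results show that the direction depends on who enters which group and on whether polish affects mild nails. Nor is it right that baseline adjustment is of no use: it recovers about half the loss.

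Other points against also stand. The primary outcome, polish compatibility, does not depend on nail involvement. The plan does not fix raw change as the analysis scale. The Background places the organisms in the subungual space particularly in early disease, so a floor removes some women to whom the rationale applies. The larger obstacle to a no-harm conclusion is 10 per group with no margin.

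None of this removes the gap. Under the assumed inputs, a 20% limit raises power on raw change, on percent change and after adjustment. Efficacy, though secondary, is in the title and the research question.

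**Conclusion.** The point holds as one about low information on change in involvement. Under the assumed inputs, a floor of 10% to 20% instead of 1% is worth about 8 to 18 percentage points of power on raw change (27% to 35% or 45%) and about 5 to 11 after baseline adjustment (36% to 41% or 47%). The size depends on how many mild nails would in fact enrol. The documents give no involvement distribution, and if few such nails enter, the loss is small. An even spread dilutes the difference; an uneven one can hide harm or create it. Even with the floor, power in the first scenario stays below 50%, so a non-significant result would not establish that polish does no harm.

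**What to change.** Add one inclusion line requiring a stated minimum percent involvement of the target nail at baseline, using the percent-involved measure already taken. Values of 10% and 20% are shown here as examples; the documents support no single value, so the investigator should choose one and give the reason.

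For women already enrolled, keep everyone and pre-specify that the comparison of percent involvement is adjusted for baseline percent involvement. Any analysis that leaves out low-involvement nails should be supportive only, since it does worse than adjustment in both settings checked.

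The cost is a one-line eligibility amendment and one sentence in the statistical section, with no new measurement. Recruitment to 20 would be somewhat slower, and the results would not cover very early disease.

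### The analysis plan covers only t-tests for a difference: yes/no and graded outcomes have no stated analysis, a non-significant result at 10 per group cannot show that polish does no harm, and week 52 compatibility answers are off treatment

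*Combined protocol and SAP*

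**What the plan says.** The closing statistical statement has two sentences: "Statistical analysis consisted of 2-tailed T-tests to study associations between continuous variables" and "P-values less than 0.05 were considered statistically significant". No other section gives a test, an interval, a margin or a rule for concluding that polish does no harm.

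The outcomes are set out in Methods.

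- **Primary outcome:** "Our primary outcome, compatibility of topical efinaconazole solution with wearing polish, will be assessed at every visit". Compatibility is asked through a "series of questions to which patients can answer yes or no" (able to apply, satisfied, tacky) and one 0–10 polish-quality item, "answered using a Likert or VAS scale where 0 represents no alteration in polish". The protocol does not say in one sentence that these four items are the primary outcome. That comes from reading the two parts of Methods together.
- **Secondary outcomes:** clinical and mycologic cure at week 52, a mild/moderate/severe grade, the onychomycosis severity index, percent of target nail involved, nail growth, and safety.

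The comparison group is "10 women who agree to abstain from wearing toenail polish during the length of the study". The trial is a "52 week study (48 weeks treatment, 4 weeks post treatment follow-up"). Visits are monthly for three months, "followed by 8-week intervals, with the final visit at week 52". Research question states the hypothesis that nail polish will not impair treatment, and sets an interim compatibility analysis at 12 weeks and a final analysis at 52 weeks.

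**The concern.** There are three gaps.

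1. **Coverage.** The t-test sentence is limited to continuous variables. Three of the four compatibility items and both cure endpoints are yes/no, and the grade is ordinal. None of these has a stated analysis, so the method could be picked after the results are seen.
2. **Decision rule.** The hypothesis is the absence of harm. The only rule given is a two-sided test for a difference at 0.05. Failing to find a difference with 10 per group is weak evidence of anything, and a large loss of cure could be reported as not significant and taken as reassurance.
3. **Timing of compatibility.** By week 52 the drug has been stopped for 4 weeks. Whether polish is tacky in the morning, or whether the woman could apply the medication, then says nothing about concurrent use. If the final compatibility result is read at that visit, it misses the question.

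**Working it through.** **Inputs.** From the documents: 10 per group (Methods); two-sided 0.05 (closing statistical statement); cure at week 52 (Methods). The plan gives no cure rate, standard deviation, power or margin, so there is no planned figure to reproduce. Every rate and SD below is an assumption. Losses are without polish minus with polish.

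**1. Can a large loss be non-significant?** Take cure in 5/10 without polish and 1/10 with polish.

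- t-test on 0/1 data: pooled variance = (10×0.5×0.5 + 10×0.1×0.9)/18 = 0.189; t = 0.4/√(0.189×2/10) = 2.06 on 18 df; p = 0.054. Barnard's test gives 0.062.
- Newcombe 95% CI: the Wilson limits are 0.237 to 0.763 for 5/10 and 0.018 to 0.404 for 1/10.
  - Lower: 0.4 − √[(0.5−0.237)² + (0.404−0.1)²] = −0.002.
  - Upper: 0.4 + √[(0.763−0.5)² + (0.1−0.018)²] = 0.676.

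An observed loss of 40 points is thus non-significant, with an interval from about 0 to 68 points. Likewise 3/10 against 0/10 gives p = 0.065 (t) and 0.088 (Barnard), CI −4 to +60 points.

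**2. How often would this happen?** Exact enumeration of all 11×11 possible results, t-test on 0/1 data, assumed true cure rates:

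| Without polish | With polish | Chance of p ≥ 0.05 |
|---|---|---|
| 20% | 0% | 88% |
| 40% | 20% | 87% |
| 40% | 10% | 71% |
| 50% | 10% | 53% |

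**3. What would identical results exclude?** With the same count in both groups, the Newcombe half-width is 28 points at 0/10 or 10/10, 34 points at 2/10 or 8/10, and 37 points at 5/10. For a difference in means, the 95% half-width is t(18)×√(2/10) = 2.101×0.447 = 0.94 SD.

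**4. Is error control lost?** Over common true rates from 0.001 to 0.999, the maximum type I error of a t-test on 0/1 data at 10 per group is 4.2%. It is not inflated.

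**5. Does the unnamed test matter?** The t-test on 0/1 data and Barnard's test give the same 0.05 decision in 121 of 121 tables. Fisher's test does not always agree: for 4/10 against 0/10, t gives 0.025, Barnard 0.042 and Fisher 0.087.

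**6. Precision in the polish group (n = 10).** Exact (Clopper–Pearson) 95% intervals are 0–31% for 0/10, 0.3–45% for 1/10, 19–81% for 5/10 and 69–100% for 10/10. For the 0–10 score the half-width is 2.262×SD/√10, or 0.7, 1.4 and 2.1 points for assumed SDs of 1, 2 and 3.

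**7. Which visits are on treatment?** Taking monthly as every 4 weeks to week 12 and then adding 8-week steps gives weeks 4, 8, 12, 20, 28, 36, 44 and 52. Treatment lasts 48 weeks, and 52 − 48 = 4 weeks off drug at the final visit. Week 48 is not on this schedule and appears only in the list of fungal tests, so week 44 is the last scheduled on-treatment visit unless the questions are also asked at week 48.

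**The case against.** The strongest reply is that the plan misapplies nothing. A reader might infer that t-tests will be run on yes/no answers, cure and the grade. The text does not say so: it confines them to continuous variables. For percent involvement, severity index and nail growth the t-test is acceptable. This stands, and the gap for the other outcomes is one of omission. Even if a t-test were used on cure, replacing it with Barnard's test would change no decision. The intervals in the working show how little 10 per group can tell, which no choice of test cures.

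A reader might also infer that the investigators will treat p ≥ 0.05 as proof of no effect. No passage says that. The protocol posits no adverse effect and defines significance, and the step between them is a risk rather than a stated rule. But nothing else in the plan offers a way to support the hypothesis, so the risk is real.

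Nor would it be right to say that no analysis time is named. Weeks 12 and 52 are given for the analyses, and week 52 for cure. The documents do not say that the week 52 analysis discards earlier compatibility answers, which are collected at every visit. What is missing is which visit answers the compatibility question on treatment.

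Finally, the hypothesis concerns efficacy, which is secondary, and n/N is the obvious summary for the polish-group items. Both are true. They narrow the decision-rule point to cure and the other efficacy outcomes, and do not remove it.

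**Conclusion.** The point holds in this form. The plan gives no analysis for the yes/no and ordinal outcomes, and its only decision rule cannot support the absence of harm at this sample size. A 40-point observed loss of cure can be non-significant, and identical results still leave roughly ±28 to ±37 points. Separately, compatibility answers at week 52 are off treatment.

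The documents do not support a charge of inflated false positives or of a t-test misused on binary data. Two readings are inferred: that the four questions make up the primary outcome, and that only the polish group can answer the tackiness and polish-quality items, since controls wear none. The figures assume 10 complete results per group, and the non-significance shares rest on assumed cure rates.

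**What to change.** 1. **Efficacy.** Report clinical and mycologic cure at week 52 as a difference in proportions with a 95% CI (for example Newcombe) as the main result. Keep the t-tests for percent involvement, severity index and nail growth, with the difference in means and its 95% CI alongside. State a summary for the severity grade. State that a non-significant p-value is not evidence of no adverse effect, and limit any such conclusion to the losses that the interval excludes.
2. **Compatibility.** In the polish group, report each yes/no item as n/N with an exact 95% CI and the 0–10 score as a mean with a 95% CI, saying whether Likert or VAS was used. Do this at week 12 and at the last on-treatment visit at which the questions are asked. Show week 52 separately, labelled off-treatment.
3. **Cure test.** Name one test in advance, because the choice can change a result. Which test is for the sponsor to choose.

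The closing statistical statement is in the past tense. If analyses have already been run, label these additions post hoc; the gain is then in reporting rather than pre-specification.

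The cost is a few lines of plan text and code, with no new patients or measurements. The downside is that the intervals will be wide and will weaken any claim that polish makes no difference. The fix makes that limit visible but does not remove it.
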